5.13 Secondary outcome measures	13
6. Study organisation and management	13
6.1 Study steering committee.....	13
6.2 Patient advocate	14
6.3 Country co-ordinators.....	14
6.4 Local co-ordinators	14
6.5 Training of investigators.....	15
7. Data management and ownership	15
8. Publication plan	15
9. References	16
10. Appendices	17

1. List of abbreviations

APRICOT	Anaesthesia PRactice in Children Observational Trial
ASOS	African Surgical Outcomes Study
ASOS-2	African Surgical OutcomeS-2 (ASOS-2) trial
EuSOS	European Surgical Outcomes Study
SAPSOS	South African Paediatric Surgical Outcomes Study

2. Summary

Short title	ASOS-Paeds
Methodology	A prospective international, multi-centre, African observational study
Research sites	Hospitals undertaking paediatric surgery in participating African countries.
Objective	To confirm the incidence of in-hospital postoperative complications in paediatric surgical patients aged < 18 years in Africa.
Number of patients	7000 patients
Inclusion criteria	All consecutive paediatric patients aged < 18 years admitted to participating hospitals undergoing elective and non-elective surgery
Exclusion criteria	Obstetric surgery
Statistical analysis	The primary outcome measure is in-hospital postoperative complications censored at 30 days postoperatively
Proposed start date	September 2021
Proposed end date	September 2022
Trial duration	Until hospital discharge, censored at 30 days

3. Introduction

Surgery is a cost-effective public health intervention. There are significant disparities in access to and the safety of surgical and anaesthesia services in low and middle-income countries (LMICs) compared to high-income countries (HICs).¹ There is a large burden of surgical disease in the paediatric surgical population with a large unmet need.^{2,3} In Africa, children comprise a significant proportion of the population with approximately 50% of the population being ≤ 19 years old.⁴

Postoperative complications are an important determinant of surgical morbidity and mortality. Limited data from Africa suggests the risk factors for, incidence and outcomes associated with paediatric surgical complications differ from HICs. In the prospective, observational South African Paediatric Surgical Outcomes Study (SAPSOS), the patients in this middle-income country (MIC),⁵ had double the incidence of complications⁶⁻⁸, and the types of complications differed from HICs, with a predominance of infective complications. Furthermore, the risk factors for complications (ASA physical status, urgency of surgery, severity of surgery and infective indication for surgery) were different from HICs, where risk factors include gestational age, ASA physical status >3 , a history of cardiovascular disease, and cardiovascular, neurological, or orthopaedic surgical procedures.⁹ Postoperative mortality was ten times higher in South Africa than in a prospective study in HICs.¹⁰ A prospective study of paediatric perioperative mortality in 24 Kenyan hospitals showed a 7 day postoperative mortality of 1.7%.¹¹, which is 17 times higher than that reported in HICs.

The African Surgical Outcomes Study (ASOS) has described surgical outcomes in adult patients in Africa.¹² Patients had a lower risk profile and fewer complications compared to those in HICs. However, the postoperative mortality was twice that of the global average.

There is a need to determine the burden of the complications in paediatric surgical patients in Africa, and the risk factors for and the type of complications experienced. If we do this, we will be able to target appropriate interventions to improve surgical outcomes for children in Africa. We have the capacity to do this important work, through the African Perioperative Research Group (APORG) group.

4. Study objectives

4.1 Primary objective

To determine the incidence of in-hospital postoperative complications up to 30 days post-surgery in paediatric surgical patients <18 years in Africa

4.2 Secondary objectives

In paediatric surgical patients < 18 years in Africa:

1. To determine the in-hospital postoperative mortality rate up to 30 days post-surgery,
2. To determine the incidence of intraoperative severe critical incidents,
3. To determine the association between pre-operative, intra-operative and facility factors with postoperative complications and death.

5. Methods

5.1 Study design

Fourteen-day, international African multi-centre prospective cohort study of paediatric patients (<18 years) undergoing surgery. This study will be registered on ClinicalTrials.gov.

5.2 Inclusion criteria

All consecutive patients < 18 years, admitted to participating hospitals during the study period who undergo elective and non-elective surgery. This will include day case surgery, operative procedures outside operating theatres where a general anaesthetic (GA) is performed. Recruitment will run for fourteen days, commencing on the date chosen by each participating hospital within the study cohort period of 01.09.2021 until 30.09.2022. Recruitment will start at 07h00 on day one and finish at 06h59 on the fourteenth day.

5.3 Exclusion criteria

1. Patients undergoing radiological or other procedures not requiring general anaesthesia, or where general anaesthesia is performed but no procedure is performed e.g. general anaesthesia during magnetic resonance imaging (MRI).
2. Patients having obstetric surgery.
3. Prior participation in the ASOS-Paeds.

5.4 Hospitals

We aim to recruit as many African hospitals as possible. Each hospital will receive an individual report allowing comparison of their dataset to that of the overall national cohort.

5.5 Research Ethics and Informed Consent

Research ethics and regulatory approvals will be sought before starting the study at each site, in accordance with national research legislation/guidelines for that country.

The national leaders will ensure the necessary ethics and regulatory approvals are obtained for the participating hospitals in their country. Hospitals will not be permitted to record data unless ethics approval or an equivalent waiver is in place.

This study is in effect a large-scale clinical audit and thus does not pose a significant risk to the study population. We expect that in most, if not every country, there will be no requirement for individual patient consent as all data will be anonymised and is already recorded as part of routine clinical care.

A precedent has already been set internationally. In the original EuSOS study, consent was waived in 27 of the 28 European countries participating¹³, in the ASOS study¹² and in the ASOS-2 trial consent was waived in the majority of hospitals. In previous African paediatric perioperative studies, written consent

was waived by six out of the eight ethics committees in the SAPSOS study⁵ and in a study in Kenya, written informed consent was waived in all 24 participating hospitals.¹¹

'Broadcasting' signage documents will be used at participating sites to ensure that all patients and parents/guardians are aware that the hospital is participating in the study. These broadcasting documents will be placed in key areas around participating hospitals explaining the study dates and the nature of the study. (Appendix 1)

5.6 Recruitment and screening

We expect all consecutive paediatric patients aged <18 years undergoing elective and non-elective surgery to be included in the study.

Broadcasting through appropriate hospital notices and signage will inform the patients, their parents/guardians and the public that the hospital is participating in the study.

Each hospital will be required to record and submit a screening log of all eligible patients.

5.7 Data collection and collation

Each individual hospital will collect and record data on either an electronic or paper case record form (CRF) for every patient recruited. Paper CRFs will be stored within a locked office in each hospital as they will include identifiable patient data in order to allow follow-up of clinical outcomes. Data will then be pseudo-anonymised by generation of a unique numeric code and transcribed by local investigators onto a secure, password protected internet based electronic CRF in the REDCap platform. Each patient will only be identified on the electronic CRF by their numeric code; thus, the co-ordinating study team cannot trace data back to an individual patient without contact with the local team. A participant (patient) list will be used in each hospital to match identifier codes in the database to individual patients in order to record clinical

outcomes and supply any missing data points. Access to the data entry system will be protected by username and password delivered during the registration process for individual local investigators. All electronic data transfer between participating hospitals and the co-ordinating centre will be encrypted using a secure protocol (HTTPS/SSL 3.0 or better).

Where individual hospitals are unable to access the internet-based case record form, pseudo-anonymised coded data may also be sent by facsimile (fax), by registered mail, e-mail or WhatsApp messaging to the coordinating centre if necessary.

Each hospital will maintain a secure study file including a protocol, local investigator delegation log, ethics approval documentation, the participant list, and other additional documentation such as study definitions.

A final summary printout of included patients with major variables should be produced for each hospital together with final data submission to double check for completeness and accuracy.

5.8 Dataset

A realistic data set will be fundamental to the success of the investigation, and this was confirmed in the EuSOS¹³, SASOS¹⁴ and SAPSOS⁵ studies where nearly complete data was available on patients. Based on the SAPSOS study of paediatric outcomes in 43 South African hospitals, we have adopted this dataset with minor changes to remove data which was found to be redundant, in order to develop a simple, lean and pragmatic data set. We believe that this simple data set will encourage hospitals to participate.

Hospital-specific data for each hospital will be collected once (Appendix 2) including: hospital level of care (first, second, third), number of operating rooms, number of specialists, number and level of critical care beds, equipment appropriate to paediatric surgery and anaesthesia, availability of medication and blood, details about the reimbursement status of the hospital and public holidays or other local factors affecting patient throughput during the study period.

5.9 Case record forms

An ASOS-Paeds CRF will be completed for every eligible patient who undergoes surgery during the cohort period (Appendix 3). Patients will be followed up until hospital discharge. This will be censored at thirty days i.e. patients will be followed up until discharge or for thirty days postoperatively if still in hospital, whichever is the shorter time period. The outcomes definition document is shown in Appendix 4.

5.10 Sample size calculation

Our plan is to recruit as many hospitals as possible from each participating country and ask them to include all eligible patients in the study. We do not have a specific sample size and statistical models will be adapted to the event rate provided by the sample recruited, in order to prevent overfitting of any logistic regression models.

5.11 Statistical analysis

The data to be collected are all collected as part of routine clinical care. Categorical variables will be described as proportions and will be compared using chi-square tests. Continuous variables will be described as mean and standard deviation if normally distributed or median and interquartile range if not normally distributed. Comparisons of continuous variables between groups will be performed using t-tests, one-way ANOVA or equivalent non-parametric tests as appropriate. Univariate analysis will be performed to test factors associated with postoperative complications, critical care admission and in-hospital death.

Single-level and hierarchical multi-level logistic regression models will be constructed to identify factors independently associated with these outcomes and to adjust for differences in confounding factors. Factors will be entered into the models based on their univariate relation to outcome ($p < 0.05$), biological plausibility and low rate of missing data.

Results of logistic regression will be reported as adjusted odds ratios (OR) with 95% confidence intervals. The models will be assessed through the use

of sensitivity analyses to explore possible interacting factors and examine any effect on the results. A statistical analysis plan will be written prior to analysis.

5.12 Primary outcome measures

Incidence of in-hospital postoperative complications in paediatric surgical patients in Africa.

5.13 Secondary outcome measures

- 1 a. The day of surgery mortality rate for patients < 18 years undergoing surgery in Africa.
 - b. The in-hospital mortality rate for patients < 18 years undergoing surgery in Africa censored at 30 days.
- 2 Risk factors associated with in-hospital complications
- 3 Time from first presentation to operation
- 4 Incidence of severe intraoperative critical incidents
- 5 Level of qualification of anesthesia and surgery providers and number of specialists per paediatric population.
- 6 Rate of admission to critical care.

6. Study organisation and management

6.1 Study steering committee

The Steering Committee will be chaired by AT. The study management team will be appointed by the Steering Committee and led by AT. The duties of this team will include administration of all project tasks, communication between project partners (including funders, Steering Committee members, national and local coordinators, etc.), data collation and management and preparation of reports for individual study sites. The Steering Committee is responsible for the scientific conduct and consistency of the project. The Steering Committee will ensure communication between the funder(s), study management team and co-ordinators as necessary.

6.2 Patient advocate

Patient advocate(s) will be appointed who will advise the Steering Committee on possible protocol amendments if required, based on patient concerns regarding delivery of the study or communication of the study.

6.3 Country co-ordinators

Country co-ordinators will be appointed by the steering committee to lead the project within individual countries and:

- Identify local co-ordinators in participating hospitals
- Assist with translation of study paperwork as required
- Ensure distribution of research manuals, and other research materials
- Ensure necessary regulatory and ethics approvals are in place prior to recruitment
- Ensure good communication with the participating sites in her/his country

6.4 Local co-ordinators

Local co-ordinators in individual institutions will have the following responsibilities:

- Provide leadership for the study in their institution
- Ensure all relevant regulatory and ethics approvals are in place for their institution
- Ensure adequate training of all relevant staff prior to data collection
- Supervise daily data collection and site recruitment and follow up management
- Act as guarantor for the integrity and quality of data collected
- Ensure timely completion of electronic CRFs

- Communicate with the relevant national co-ordinator

6.5 Training of investigators

Training will be done using instructional videos placed on the study website. Each study site will be required to complete an online questionnaire as part of the site initiation, prior to starting data collection.

7. Data management and ownership

On behalf of the Steering Committee, the Department of Anaesthesia and Perioperative Medicine, Groote Schuur Hospital and University of Cape Town will act as custodian of the data. The Steering committee will retain the right to use all pooled data for scientific and other purposes. Members of the ASOS-Paeds study group will have the right to access the pooled data for research purposes provided the research proposal has been reviewed and deemed appropriate by the Steering Committee. The primary consideration for such decisions will be the quality and validity of any proposed analysis. Only summary data will be presented publicly, and all institutions will be anonymised except in the individualised report provided to each institution at the end of the study. Individual patient data provided by participating sites remain the property of the respective institutions.

8. Publication plan

Data will be presented and disseminated in a timely manner. The Steering Committee will appoint a writing committee to draft the scientific report(s) of this investigation. The group will be known as 'The ASOS-Paeds Investigators'. It is anticipated that a number of secondary analyses will be performed. ASOS-Paeds investigators will be given priority to lead such analyses and are encouraged to do so. Participation and authorship opportunities will be based on contribution to the primary study. On request, hospitals will be provided with an individual report allowing comparison of their

Appendix 1 – Broadcasting document

Appendix 2 – Hospital Information and site initiation record form

Appendix 3 – Case record form (CRF)

Appendix 4 – Outcomes definitions document

Table 1. Description of cohort including patient, surgical, anaesthesia and facility characteristics	9
Table 2: The categories and types of intra-operative severe critical events	11
Table 3. Univariable and multivariable analysis of preoperative factors associated with intra-operative severe critical events.....	12
Table S1: Intra-operative severe critical events by facility and anaesthesia provider	14
References.....	16

Introduction and rationale for the “severe critical events” analysis

Universal Health Coverage aims to guarantee access to needed health care services for all people without financial burden, which includes surgical service delivery. (1) The World Health Assembly resolution EB152(3), stated “integrated Emergency Critical Operative Care for universal health care (ECO-UHC) and protection from health emergencies” should be part of global health improvement interventions. It advocates for the delivery of quality health care for acutely ill people. This includes early access and intervention for general acute childcare including operative care. This is particularly important in low and middle income countries because the proportion of child population is estimated to be half of the total population. (2)

Paediatric mortality after surgical procedures continues to be high. One study reported a mortality of 12%, with oesophageal atresia accounting for 72% and jejunoileal atresia for 35%. (3) The human resources available for paediatric surgery are limited, with a low number of paediatric surgeons and paediatric anaesthesiologists compared to the burden of the paediatric surgical population. The result is that in many places non-specialists and even other non-physician professionals might be solely responsible for peri-operative care. (4, (5)) This can result in excess intra-operative critical events. Critical events are however, inadequately investigated in Africa. The existing data are derived from registries which are often incomplete and may not target critical events.

Intraoperative critical events can have multiple risk factors and contribute to anaesthesia related complications. The incidence ranges from 2.32% to 11.7% and shows significant variability among different settings. The largest intraoperative critical event study in Europe showed a high number of intraoperative severe critical events (5.2%) with significant variability between hospitals. Respiratory critical events were the most common (3.1%) followed by cardiovascular instability (1.9%). The immediate poor outcome was 5.4%. (6)

There are specific considerations that should be sought in Paediatric population anaesthesia related critical events. These may include the choice of drug and their response. Additionally, the anaesthesia related adverse effects may have long term sequelae for children. As a result, studying those critical events will help to identify the factors related and final outcomes which will help in standardizing the care. It will also be a base to advocate for intraoperative care.

Reported incidences from high income countries

Studies from Europe reported incidences ranging from 0.14% for serious adverse events to 3.4% for critical incidents. (7) Similarly a study done by Cohen et al showed a severe anaesthesia critical event rate of 1.4 per 1000. The commonest events were respiratory followed by cardiac. (8) A large international multicentric cohort study covering North America, Oceania and Europe reported an incidence of 24 % for intraoperative adverse events. (9)

Reported incidences from low- and middle-income countries

The reported incidences for critical events vary across low and middle-income countries (LMICs). A South Korean study reported a 0.4% incidence of paediatric anaesthesia related critical incidents, with respiratory events been the commonest (55% of the cases), (10) compared to an Indian study which reported a 12% incidence, predominated by respiratory complications. (11) Generally, LMICs may carry at least double the burden of intraoperative critical events to high-income countries, although the risk should be similar to that of HICs. These excess events should be preventable. (12)

Types of complications

Respiratory related complications are most commonly reported, followed by cardiovascular events.

Risks associated with complications

The following patient and surgical risk factors have been shown to contribute to intraoperative critical events: age <1 year, ASA physical status III and IV, urgency of the surgical procedure, and preexisting comorbidities. The level of training of the anaesthesia providers and the number of years of experience, as well as the type of anaesthesia and surgery done are potentially important risk factors. (13)

Study rationale

African Surgical Outcomes Study in Paediatric patients (ASOS-Paeds) determined the incidence of in-hospital postoperative complications up to 30 days after surgery in paediatric surgical patients across different hospitals in Africa. This study will evaluate the intra-operative critical incidents reported in ASOS-Paeds. It is hoped that these findings will contribute to improving perioperative care for paediatric surgical patients in Africa.

Aims and objectives of the “severe critical incidents” analysis

Aims

The aims of this study are to describe the incidence of intraoperative severe critical events, the types of severe critical events, and risk factors independently associated with severe critical events.

Objectives of the study

Primary objective

1. To describe the incidence of intra-operative severe critical events in paediatric surgical patients in Africa

Secondary objectives

1. To describe the categories and types of severe critical events
2. To identify risk factors independently associated with severe critical events

Sensitivity analyses

1. Two sensitivity analyses will be conducted:
 - a. The sensitivity analyses of elective surgical patients, and emergency surgical patients, and
 - b. A sensitivity analysis excluding the two countries providing more than 10% of the patients to the dataset (Egypt and South Africa)

Statistical Analysis Plan

A) Data Validation

- Report on the number of incomplete data points
- Report on primary outcome data
 - % missing data for incidence of severe critical events
- Provide STROBE diagram of recruited patients

B) Statistical tests

- Categorical variables will be described as number and proportions (percentage) and will be compared using appropriate Chi-squared or Fisher's exact tests.
- Continuous variables will be calculated and reported as mean and standard deviation (SD) if normally distributed, or median and inter-quartile range (IQR) if not normally distributed.
- Comparisons of continuous variables between groups will be performed using t-tests, one-way ANOVA or equivalent non-parametric tests as appropriate.
- If $< 5\%$ of data are missing for the primary outcomes, a complete case analysis will be conducted
- A p-value of less than 0.05 will be considered statistically significant for all analyses
- Generalized mixed effects model analysis will be performed for exploration of candidate variables for prediction of risks for the primary outcome i.e. incidence of severe critical events
 - Further description to follow in the section discussing risk prediction
- Sensitivity analyses will be conducted.

C) Primary objective

1. To describe the incidence of intra-operative severe critical events in paediatric surgical patients in Africa

This will be presented as number (n/N), percentage (%)

The cohort will be described according to the variables (Table 1)

- Age, ASA PS, sex
- Comorbidities
- Describe the Hospital, Surgery and Anaesthesia information
 - Hospital level
 - Urgency of surgery (elective, emergency)
 - Severity of surgery (minor, intermediate, severe),
 - Indication for surgery
 - Type of surgery
 - Intraoperative factors
 - Most senior anaesthetist
 - Most senior surgeon

- Time of induction

D) Secondary objectives

1. To describe the categories and type of intra-operative severe critical events
 - Outcome definitions are defined in the study protocol
 - The categories of severe critical events will be presented as airway, respiratory, cardiovascular, metabolic, and other severe critical events categories (Table 2) using % to indicate the incidence (number of patients with severe critical events divided by the number of patients) and 95% confidence intervals.
 - To describe the types of severe critical events within each category
 - The categories and types of severe critical events will also be presented by the level of facility, and the level of the anesthesia providers (Table S1)
2. To identify risk factors independently associated with severe critical events
 - All variables will be entered into the model, unless there are less than 10 events per variable. If this is the case, risk factors with a p value ≤ 0.05 for severe critical events identified by univariate analysis will be entered into the model. (Table 3) The reference category for the surgical discipline will be decided by the surgical discipline with the lowest incidence of severe critical events
 - Results will be presented as unadjusted and adjusted odds ratios (ORs) with 95% confidence intervals (CI's).

Analyses will be conducted using Statistical Package for the Social Sciences (SPSS) version 30 (SPSS Inc., Chicago, IL, USA) and R: A language and environment for statistical computing. Vienna, Austria: R Foundation for Statistical Computing (2024) using Studio: Integrated Development Environment for R. Boston, MA: RStudio, Inc. (2024).

Tables

Table 1. Description of cohort including patient, surgical, anaesthesia and facility characteristics

		All patients (n=)	Patients with severe critical events (n=)	Patients without severe critical events (n=)
		n/N (%)	n/N (%)	n/N (%)
Age	Mean (SD) Median (IQR)			
Sex				
Male				
Female				
Age categories				
0-28 days				
29 days to < 1 yr				
1 to < 4 yr				
4 to < 13 yr				
13 to <18 yr				
ASA PS				
I				
II				
III				
IV-V				
Urgency of surgery				
Routine				
Emergency				
Severity of surgery				
Minor				
Intermediate				
Major				
Primary indication for surgery				
Non-communicable disease				
Infective				
Trauma				
Congenital				
Hospital level				
First				
Second				
Third				
Most senior anaesthetist				

Specialist			
Non-specialist physician			
Nurse			
Non-physician			
Most senior surgeon			
Specialist			
Non-specialist physician			
Nurse			
Non-physician			
Type of surgery			
Orthopaedic			
Cardiac			
ENT			
Gynaecological			
Hepatobiliary			
Kidney/urological			
Gastrointestinal			
Thoracic			
Ophthalmology			
Maxillo-facial/ dental			
Plastic/cutaneous			
Neurosurgery			
Burns			
Comorbidities			
Cardiac disease			
Chronic respiratory disease			
Neurological disorder			
HIV/AIDS			
Cancer			
Current respiratory tract infection			
Intraoperative factors			
Duration			
Surgical checklist used			
Time			
Daytime			
After hours			

Table 2: The categories and types of intra-operative severe critical events

	Overall	Incidence
	n/N (%)	% (95% CI)
Categories of anaesthetic severe critical incidents		
Any		
Any Airway/respiratory		
Any CVS		
Any Other		
Types of severe critical events by category		
Airway/respiratory		
Difficult BMV		
Difficult Intubation		
Failed Intubation		
Laryngospasm		
Bronchospasm		
Aspiration		
Severe Hypoxia		
CVS		
Bradycardia		
Cardiovascular instability		
Cardiac Arrest		
Metabolic		
Temp < 36		
Low Glucose		
Other		
Anaphylaxis		
Drug error		
Death		
Yes		
No		

Table 3. Univariable and multivariable analysis of preoperative factors associated with intra-operative severe critical events

	Univariable		Multivariable	
	OR (95% CI)	p-value	OR (95% CI)	p-value
Age (per 1 year)				
Sex				
Male				
Female	Reference			
ASA PS				
I	Reference			
II				
III				
IV-V				
Urgency of surgery				
Routine	Reference			
Emergency				
Severity of surgery				
Minor	Reference			
Intermediate				
Major				
Primary indication for surgery				
Non-communicable disease	Reference			
Infective				
Trauma				
Congenital				
Hospital level				
First				
Second				
Third	Reference			
Most senior surgeon				
Specialist	Reference			
Non-specialist physician				
Nurse				
Non-physician				
Most senior anaesthetist				
Specialist	Reference			

Non-specialist physician				
Nurse				
Non-physician				
Type of surgery				
Orthopaedic				
Cardiac				
ENT				
Gynaecological				
Hepatobiliary				
Kidney/urological				
Gastrointestinal				
Thoracic				
Ophthalmology				
Maxillo-facial/dental				
Plastic/cutaneous				
Neurosurgery				
Burns				
Comorbidities				
Cardiac disease				
Chronic respiratory disease				
Neurological disorder				
HIV/AIDS				
Cancer				
Current respiratory tract infection				
Intraoperative factors				
Duration				
Surgical checklist used	Reference			
Surgical checklist not used				
Time				
Daytime	Reference			
After hours				

Table S1: Intra-operative severe critical events by facility and anaesthesia provider

	Hospital level			Most senior anaesthetist			
	District	Regional	Tertiary	Specialist	Non-specialist physician	Nurse	Non-physician
Categories of anaesthetic severe critical incidents							
Any							
Any Airway/respiratory							
Any CVS							
Any Other							
Types of severe critical events by category							
Airway/respiratory							
Difficult BMV							
Difficult Intubation							
Failed Intubation							
Laryngospasm							
Bronchospasm							
Aspiration							
Severe Hypoxia							
CVS							
Bradycardia							
Cardiovascular instability							

Cardiac Arrest							
Metabolic							
Temp < 36							
Low Glucose							
Other							
Anaphylaxis							
Drug error							
Death							
Yes							
No							

References

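### Table 3 of the SAP models age as one linear term per year, so it gives no direct adjusted estimate for children under 1 year, the first risk factor the SAP names

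*SAP*

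**What the plan says.** The SAP, under Risks associated with complications, states "The following patient and surgical risk factors have been shown to contribute to intraoperative critical events" and then lists "age <1 year, ASA physical status III and IV, urgency of the surgical procedure, and preexisting comorbidities". Age therefore appears as a threshold at 1 year.

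Table 1 ("Description of cohort including patient, surgical, anaesthesia and facility characteristics") has five age categories. Two lie below 1 year: 0-28 days and "29 days to < 1 yr".

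Table 3 ("Univariable and multivariable analysis of preoperative factors associated with intra-operative severe critical events") has one age row, per 1 year, with no bands and no reference level. The same row serves the univariable and multivariable columns.

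Section D, item 2 sets the entry rule: "All variables will be entered into the model, unless there are less than 10 events per variable". Below that limit, only factors with univariate p ≤ 0.05 enter.

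No spline, polynomial or linearity check is mentioned. Of the two sensitivity analyses, one is "The sensitivity analyses of elective surgical patients, and emergency surgical patients" and the other excludes Egypt and South Africa. Protocol section 5.11 speaks of sensitivity analyses only for interacting factors.

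**The concern.** The second secondary objective is to find independent risk factors. One odds ratio per year in a logistic-type model makes the log-odds linear in age. If the excess risk is concentrated in infancy, that term understates it and creates a falling trend through later childhood that need not exist. The model will return an odds ratio between any two ages, but each is dictated by the one slope, so the under-1 contrast is not estimated in its own right.

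Three things are at stake:

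- **The infant estimate.** Table 1 shows only the crude split by event status. It cannot separate infancy from ASA status, congenital indication or type of surgery.
- **The fallback screen.** If the 10-events rule is triggered, age must pass a univariate test in this linear form, and a real infant effect is then easier to miss.
- **Other coefficients.** If high ASA status and congenital indication are commoner in infants, some age confounding stays in those estimates. This is conditional, and near zero if they are unrelated to age.

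**Working it through.** The plan gives no figure for the age effect, so there is none to reproduce. What follows is an illustration.

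**Inputs from the documents.** 7000 patients (Protocol section 2, although section 5.10 sets no specific sample size). Incidence 5.2% (the European study quoted in the SAP introduction). For the range, the SAP says "The incidence ranges from 2.32% to 11.7% and shows significant variability among different settings".

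**Assumptions.** Shares in the five Table 1 bands 6/14/22/40/18%, so 20% are under 1 year; age uniform within bands. True odds ratio (OR) 2 in both infant bands and 1 afterwards. The models are fitted to expected risks, so there is no simulation error. The other Table 3 covariates and the mixed-effects structure are left out.

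**Linear fit, age alone.** Model: logit(p) = α + β × age, so OR(a vs b) = k^(a − b) with k = exp(β). The fit gives k = 0.964 (0.9644 before rounding), z = −3.5.

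| Contrast | Calculation | Implied OR | True OR |
|---|---|---|---|
| 6 months vs 8.5 years | 0.9644^(−8) | 1.34 | 2.0 |
| 6 months vs 2.5 years | 0.9644^(−2) | 1.08 | 2.0 |
| 15.5 vs 8.5 years | 0.9644^7 | 0.78 | 1.0 |

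The five bands return 2.0, with a 95% CI of 1.50 to 2.67 for 29 days to under 1 year. They raise twice the log-likelihood by about 20 for three extra coefficients. If ASA status and congenital indication are added and made to track age, the linear fit gives about 0.97 per year (z = −2.9) and 1.30 for the first contrast.

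**Sensitivity of the first contrast (true 2.0), across fits with and without that link:**

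- 10% to 30% under 1 year: 1.18 to 1.42.
- Incidence 2.32% to 11.7%: 1.28 to 1.34.
- Gradual decline (OR 2 in both infant bands, then 1.5, 1, 0.8): 1.56 to 1.59. The log-likelihood gain from bands falls to about 6.

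**Chance of passing the univariate screen** (linear on 1 df, bands on 4 df, other factors unrelated to age):

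| Scenario | Linear | Bands |
|---|---|---|
| OR 2, 5.2% | 0.95 | 1.00 |
| OR 2, 2.32% | 0.69 | 0.90 |
| OR 1.5, 5.2% | 0.50 | 0.73 |

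If ASA and congenital indication track age, the last row becomes 0.90 vs 0.99.

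**Conditional confounding.** Assume high ASA prevalence of 60/30/15/12/12% and congenital indication of 75/55/35/15/8% across the bands. With linear age, the ASA OR is then 2.24 (true 2.0) and the congenital OR 1.13 (true 1.0), each off by about one standard error (0.12). With gradual decline they are 2.10 and 1.07. If unrelated to age they are 1.99 and 1.00.

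**Coefficient count for Table 3.** Age 1, sex 1, ASA 3, urgency 1, severity 2, indication 3, hospital level 2, surgeon 3, anaesthetist 3, type of surgery 12, comorbidities 6, duration 1, checklist 1, time 1: total 40. Bands make it 40 − 1 + 4 = 43. Events: 7000 × 0.052 = 364. Then 364/40 = 9.1 and 364/43 = 8.5 events per coefficient.

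**The case against.** A per-year age term is conventional, and the model is described as exploring candidate variables for a secondary objective. The primary objective, incidence, is untouched. Naming age under 1 year as a risk factor does not say that risk steps down at 1 year and is flat afterwards; it fits a continuous decline equally well. If age is truly log-linear there is no bias, and bands cost precision. In the base case the linear term still flags younger age, and Table 1 lets a reader compute the crude infant odds ratio.

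All of this stands, and it sets the weight of the point. It does not remove it: the plan offers no check of the linear form, and the infant contrast was understated both under a step and under a gradual decline.

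A cheaper remedy is to keep the linear term and add one indicator for under 1 year (41 coefficients, 364/41 = 8.9 events each). Under a pure step this captures the whole log-likelihood gain. Under the gradual decline it gains only 3.5 against 6.4 for the bands, so it is a reasonable second choice but does not displace them.

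The confounding figures rest on assumed prevalences and should carry little weight.

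**Conclusion.** The concern holds. The SAP names infancy as a risk factor, defines the bands needed to study it, and then uses a form of age in its only regression table that cannot show it properly. In the illustration a true odds ratio of 2.0 appears as 1.18 to 1.42 under a step at 1 year and as 1.56 to 1.59 under a gradual decline. The step also produces a false gradient in older children. These sizes depend on the assumed age mix and effect, which the documents do not give, and on a model simpler than Table 3; the size of the distortion in the full model is unknown. The conclusion about the primary outcome does not change. The correction is worth making because it is cheap.

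**What to change.** In Table 3, replace the per-year row with the five Table 1 age categories (reference 4 to under 13 years) in both the univariable and multivariable columns. Alternatively, adjust with a restricted cubic spline that has a knot in the first year, and report the infant contrast from it. Keep age in the model whatever its univariate p-value. State whether the 10-events rule counts coefficients or table rows, and count the added age terms under it.

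**Cost.** A table-shell edit and one sentence.

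- Counted by coefficient, the rule needs 400 events now (400/7000 = 5.71%) and 430 with bands (6.14%), so the swap changes the branch only between those two totals. At 364 events the model is below 10 per coefficient either way.
- Counted by row (19 rows, 364/19 ≈ 19 events each), nothing changes.
- If age is truly log-linear (assumed OR 0.96 per year), the standard error of the log OR for infants against 8.5 years rises from about 0.09 to 0.16–0.17. Univariate power for age falls from 0.98 to 0.88. The ASA and congenital estimates are unaffected.
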